4.4 Early Withdrawal of Subjects

4.4.1 When and How to Withdraw Subjects

Patients will be withdrawn from the study prior to completing all study related procedures if:

- Disease progression
- Intolerable adverse effects

- Patient decision to withdraw from the study
- Failure to adhere to protocol requirements, including refusal of surgery and noncompliance to letrozole \geq 5 consecutive days.

4.4.2 Data Collection and Follow-up for Withdrawn Subjects

A patient is deemed a withdrawal if he/she is removed from the study for any reason before any study treatment is given. On-study material and the End of Active Treatment/Cancel Notification Form must be submitted. No further data submission is necessary.

5 Study Drug

5.1 Description

Letrozole is a standard of care aromatase inhibitor used to treat hormone receptor positive breast cancer.

5.2 Treatment Regimen

Letrozole 2.5 mg oral daily dose will be used for 2-8 weeks prior to surgery.

5.3 Drug Accountability

Drug accountability will be performed via patient pill diaries and patient appointments.

6 Study Procedures

This is a prospective study to collect tissue samples from patients with early-stage hormone receptor-positive HER2-negative breast cancer. Patients with newly diagnosed hormone receptor-positive HER2-negative invasive breast cancer will be approached by the study team prior to surgery. Once pathology confirms the diagnosis for hormone receptor-positive HER2 negative invasive breast cancer, the patient will be evaluated by breast surgeons. If there is no indication for neoadjuvant therapy and the patient can proceed with surgery within 2-8 weeks, the patient will be considered registered and start on aromatase inhibitor with letrozole 2.5 mg oral daily for 2-8 weeks until surgery as part of their standard of care. Patients will take letrozole until within 48 hours prior to surgery. Both archival biopsy and surgical specimens will also be collected for single-cell sequencing.

Peripheral blood will be drawn at two timepoints: 1.) prior to letrozole treatment and 2.) at least two weeks after the start of letrozole treatment, but prior to surgery.

Estrogen receptor, progesterone receptor, HER2, and Ki-67 will be evaluated in both biopsy and surgical specimen as per standard of care. Tumors with persistent elevation of Ki-67 \geq 10% after

2-8 weeks of letrozole will be classified as non-responders, and tumors with Ki-67 < 10% after treatment will be classified as responders.

This study is not utilizing the Cancer Center Registration Application. Patients will be considered enrolled upon completion of the ICF in PTrax. However, patients will not be considered registered within the Cancer Center until they have met all eligibility criteria and have a status of accrued in PTrax.

6.1 Test Schedule

Tests and Procedures	Screening	Baseline (Day 1 of Letrozole)	After 2-8 weeks of Letrozole	Surgery ²
Visit Window	-30 days from baseline	-7 days		
Standard of Care Procedures				
Consent	X			
History and Physical		X	X ⁵	
Adverse event assessment		X	X ⁵	
Tissue collection	X ¹			X ¹
Research Procedures				
Blood samples		X ³	X ³	
- Sodium heparin (green top)				
10 mL x 6 tubes				
- Serum (red top) 10 mL x 1 tube				

¹ Archival sample collection from the standard of care biopsy and surgical resection at least 5 x 5 uM slides will be collected.

² Surgery should occur less than 48 hours after the last dose of letrozole.

³ Completed at two timepoints: 1.) prior to letrozole treatment and 2.) at least two weeks after the start of letrozole treatment, but prior to surgery.

6.2 Sample Processing

All biopsy and surgical specimens will be snap frozen by BAP/PRC or CRC team. Samples will be kept at -80°C and held for pick up.

Blood samples will be processed by BAP/PRC. PBMC, serum, and plasma will be aliquoted, kept at -80°C, and held for pick up.

Statistical Plan

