1.1 Background

In-depth transcriptomic analysis for each subpopulation in the tumor microenvironment of pre-treatment and post-treatment tumor samples obtained from AI-sensitive vs. AI-resistant patients will be performed using single-nucleus RNA-sequencing (snRNA-seq) (Figure 1). Re-clustering of stromal cells into sub-clusters will be undertaken to uncover hidden transcriptomic heterogeneity and to identify transcription factor regulation signatures that define these sub-clusters. Validation of transcriptome data will be performed using qPCR and immunofluorescence staining of cultured flow-sorted cells from human tissue sections and immunohistochemistry of these sections. We also seek to study the interactions between spatially distinct stromal sub-clusters and other cells (tumor, immune and endothelial) that will be studied by annotating our dataset with curated human ligand-receptor pairs. In turn, this will shed light on the role of stromal sub-clusters on modulating immune activation vs. tolerance/evasion via recruitment/exclusion and/or (dys)regulation (exhaustion/activation) of specific immune subpopulations including Tregs, cytotoxic T cells, and tumor-associated macrophages. Furthermore, peripheral blood will also be collected at baseline and after AI treatment to evaluate systemic changes of immune response after AI in responders vs. nonresponders.

[figure not shown]

Figure 1. The schematic representations of the study: The collection of pre-treated biopsies from breast cancer patients with estrogen receptor positive (ER+) and human epidermal growth receptor 2 negative (HER2-) is shown. The obtained surgical specimens from good responders and bad responders (progressors) will be analyzed and compared with pre-treated samples. All analyses will be carried out through single nucleus RNA-sequencing.

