We had experience working with patient samples with triple-negative breast cancer (TNBC). The purpose of the study is to show the impact of different combinations of chemotherapeutics on tumor microenvironment remodeling in bad responders (chemotherapy-resistant). Trichrome staining (a staining method to detect total collagen) was performed on both biopsies (before treatment) and surgical specimens (after treatment), which were obtained from the same patients, to compare the collagen expression level. Our findings showed that chemotherapeutics cause fibrosis, represented by higher collagen expression in the surgical specimens in comparison to collagen expression in biopsies (Figure 2) (1,2).

[figure not shown]

Figure 2. Trichrome staining of samples obtained from disease progressor patients with TNBC: Representative images show that different combination chemotherapy causes an increase in collagen content in the tumor microenvironment (*p<0.01).

subpopulations in doxorubicin (dox) sensitive vs. resistant murine TNBC models. For this study, doxorubicin-resistant murine triple-negative 4T1 cells were developed and inoculated into a mouse mammary fat pad. Tumors were taken, fibroblasts were isolated and analyzed with 10x genomics single-cell RNA-sequencing. Our findings showed that the fibroblasts which were isolated from dox-resistant tumors activated overexpression of collagen-related genes (Figure 3).

There have been several studies addressing the issues on the impact of chemotherapeutics on different cell populations in breast tumors (3, 4). The amount of infiltrated immune cell populations into breast tumors, for example, has been strongly related to the response to chemotherapy (5). However, not much is known about the impact of AIs on the cell populations of breast tumors. A very appreciated effort from Miller and colleagues reported their findings on patients who developed letrozole resistance (6). This study, however, was unfortunately limited by bulk RNA-based gene expression profiling.

In our project, by the help of single nuclei RNA-sequencing, we will be able to analyze the expression profile of the different type of tumor cell populations before and after letrozole treatment. This will provide an intensive analysis identifying novel markers predicting for response and understanding molecular mechanisms of resistance.

[figure not shown]

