4.1 Inclusion Criteria

Screening inclusion criteria

1. Female \geq 18 years.
2. Postmenopausal and suitable to receive aromatase inhibitor as per physician's discretion.
3. Histologically confirmed un-resected operable invasive adenocarcinoma of the breast ≥ 0.5 cm with estrogen receptor (ER) and/or progesterone receptor (PR) positive $\geq 10\%$, and no human epidermal growth factor receptor 2 (HER2) amplification or overexpression.
4. Patients must not have received any prior chemotherapy, radiation therapy, or endocrine therapy for their current breast cancer. Patients who received tamoxifen or raloxifene or another agent for prevention of breast cancer may be included.
5. Willing and able to provide research tissue samples.
6. Willing and able to provide research blood samples.

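### Healing after the diagnostic biopsy is mixed with any letrozole effect in the surgical-versus-biopsy comparison, and the plan records nothing that would show by how much

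*Combined protocol and SAP*

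**What the plan says.** Eligibility (section 4.1) requires "Histologically confirmed un-resected operable invasive adenocarcinoma of the breast ≥ 0.5 cm", so the tumor has been sampled once before entry. Section 5.2 then states: "Letrozole 2.5 mg oral daily dose will be used for 2-8 weeks prior to surgery". Section 6 adds that "Both archival biopsy and surgical specimens will also be collected for single-cell sequencing".

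The tissue instructions are short. Note 1 of section 6.1 specifies "Archival sample collection from the standard of care biopsy and surgical resection" with a minimum number and thickness of slides. Section 6.2 specifies that "All biopsy and surgical specimens will be snap frozen by BAP/PRC or CRC team" and kept at -80°C. Neither gives a position within the tumor, a distance from the biopsy site, or a histology check of the piece that is sequenced. Statistical Methods (under 6.3) names no covariate. Nothing asks for tumor size or the biopsy-to-surgery interval to be recorded for the analysis.

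On read-outs, section 1.1 says "Re-clustering of stromal cells into sub-clusters will be undertaken to uncover hidden transcriptomic heterogeneity", and it also lists regulatory and cytotoxic T cells and tumor-associated macrophages. Figure 1 describes surgical specimens of good and bad responders compared with pre-treatment samples. Sub Aim 2B concerns the effect of estrogen deprivation on the tumor immune microenvironment. No untreated pairs of biopsy and resection are described.

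**The concern.** A biopsied tumor contains a healing track when it is resected. Fibroblasts, collagen and macrophages are prominent in healing tissue; that is general pathology and is not stated in the documents. These are also the cells the study measures. A surgical piece that includes part of the track will differ from the earlier biopsy of the same tumor even if letrozole does nothing.

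The plan cannot separate the two explanations by design, because all patients are biopsied and all are treated. It also cannot examine the question afterwards, because the position of the piece is not kept. The interpretation of stromal and immune shifts under Sub Aim 2B is at stake. So, conditionally, is the comparison of surgical specimens by response group under Aim 1.

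The team's preliminary work shows how easily this reading arises. In treated triple-negative tumors it reports "higher collagen expression in the surgical specimens in comparison to collagen expression in biopsies" and attributes the difference to chemotherapy. The same alternative explanation was open there.

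**Working it through.** The protocol gives no power, effect size or variance, so there is no figure of its own to reproduce. The checks below are illustrative, and each assumed input is marked.

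**1. Biopsy-to-surgery interval (documents: 2-8 weeks of letrozole; 30-day screening window).**
- Minimum: 2 × 7 = 14 days.
- Maximum on letrozole: 8 × 7 = 56 days.
- With a biopsy at the start of screening: 56 + 30 = 86 days, about 12 weeks. It is longer if the archival biopsy is older.

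**2. Share of the tumor affected (document: 0.5 cm minimum; assumed: spherical tumor, one central pass, affected width 2a).** Share = 1 − (R² − a²)^1.5 / R³. For R = 2.5 mm and a = 1 mm this is 1 − 5.25^1.5 / 15.625 = 0.23.

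| Affected width | 5 mm tumor | 10 mm tumor | 20 mm tumor |
|---|---|---|---|
| 1 mm | 6% | 1.5% | 0.4% |
| 2 mm | 23% | 6% | 1.5% |
| 3 mm | 49% | 13% | 3.4% |
| 4 mm | 78% | 23% | 6% |

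With 2 to 6 cores of 1.6 mm diameter near the centre (assumed), simulation puts 70-95% of a 0.5 cm tumor in or within 1 mm of a track, against 7-13% of a 2 cm tumor. Varying core placement widens these to 63-100% and 8-18%. The percentages depend on the assumptions; the steep fall with size does not.

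**3. Before/after comparison.** Let q be the share of surgical pieces containing track tissue and h the change that track tissue makes to a cell fraction. The false shift is q × h. With q = 30% and h = 30 points (both assumed) it is 0.30 × 30 = 9 points. It does not cancel, since only the surgical specimen follows the biopsy.

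**4. Response-group comparison of surgical specimens.** The false difference is (q in non-responders − q in responders) × h.
- Equal q: 0.
- Assumed 50% versus 20%, h = 30 points: 0.30 × 30 = 9 points.
- Chance alone: with equal true q of 10-50% and 10 to 25 non-responders among 50 (assumed), the exact binomial probability that non-responders have a share at least 20 points higher is 2-15%.

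**5. Systematic route through tumor size.** Assumed: 4 cores, median size 1.5 cm (log SD 0.6, truncated at 0.5 cm), 25% non-responders, random sampling of the resection, a 1-2 mm reaction zone, and a cell type 3 times as frequent in reaction tissue. The responder/non-responder ratio is (1 + 2 × share in responders) / (1 + 2 × share in non-responders). At a correlation of 0.3 between size and post-treatment Ki-67:
- 1 mm zone: (1 + 2 × 0.242) / (1 + 2 × 0.159) = 1.484 / 1.318 = 1.13.
- 2 mm zone: (1 + 2 × 0.439) / (1 + 2 × 0.304) = 1.878 / 1.608 = 1.17.

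| Correlation of size with Ki-67 | Spurious ratio | With other core placements |
|---|---|---|
| 0 | 1.00 | 1.00 |
| 0.2 | 1.09-1.11 | 1.10-1.12 |
| 0.3 | 1.13-1.17 | 1.16-1.17 |
| 0.4 | 1.18-1.23 | 1.22-1.25 |

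The ratio is responder over non-responder. If larger tumors are more often non-responders, the excess of healing tissue falls in the responders. The interval is not in this model.

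**The case against.** **Both groups are biopsied, so the effect cancels.** This stands for the response-group comparison when track share is equal in the two groups: the expected bias is then zero. It does not help the before/after comparison.

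**Healing tissue would be mistaken for the microenvironment of AI resistance.** A reader might infer this, but the documents do not support it. They do not say how size or interval relates to response, and under the size mechanism modelled here the excess appears in AI-sensitive tumors. That would mask or reverse a stroma-rich resistance signal rather than create one.

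**Nothing can be recovered later.** This too goes further than the documents allow. Tumor size and procedure dates should be in the clinical chart. Slides are collected from both specimens, and section 1.1 plans staining of tissue sections, which might serve as a partial histological check. What is lost is the position of the frozen piece.

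**Aim 1 does not rest on resections alone.** Correct. Section 1.1 covers pre-treatment and post-treatment samples, and section 2 hypothesises pre-existing resistance mechanisms. Comparing diagnostic biopsies by response group serves that hypothesis and is free of this problem. Sections 3.4 and 6.3 do not define the primary comparison as resection against resection.

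**The magnitude is assumed.** Also correct. The documents say biopsy without giving a needle type or number of passes, and the most striking shares belong to tumors at the eligibility floor. For scale, if the between-patient SD of a log cell fraction is 0.5 with 12 versus 38 patients (assumed), the standard error is 0.5 × √(1/12 + 1/38) = 0.166. Ratios of 1.13 and 1.17 are then 0.74 and 0.95 standard errors.

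**Conclusion.** The concern holds in a limited form. In the surgical-versus-biopsy comparison (Figure 1, Sub Aim 2B), healing and letrozole are confounded by design, and the plan as written lets a healing response count as an effect of estrogen deprivation. In the AI-sensitive versus AI-resistant comparison of surgical specimens there is bias only if track share differs by response group, whether through tumor size, interval or chance, and its direction is not fixed. The comparison of diagnostic biopsies by response is unaffected.

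The size cannot be computed from the documents. Under the assumed inputs the spurious response-group ratio runs from 1.00 (size unrelated to Ki-67) to about 1.25. The before/after shift is 9 points in the example with 30% of pieces affected and a 30-point change. This is a low-cost improvement to a pilot, worth making early because position cannot be reconstructed once a piece is frozen without a record.

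**What to change.** **Section 6.2 and note 1 of 6.1.** Mark each surgical research piece as near or away from the biopsy site, by a rule written down beforehand. Prefer viable tumor away from the site where tumor size allows.

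**REDCap.** Enter the near/away mark, pathologic tumor size, and days from biopsy to surgery.

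**Statistical Methods.** Show tumor size and interval by response group. Repeat the surgical comparison by response, and the before/after comparison, without pieces marked near the biopsy site. State that before/after stromal or immune shifts which disappear in that analysis will not be attributed to estrogen deprivation alone.

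**Cost.** One tissue-handling instruction, three data fields and one repeated analysis, with no new procedure and no change to eligibility. The repeated analysis will have fewer patients and will mainly lose small tumors. Sampling away from the track can also move small tumors toward their periphery, which is a size-dependent position effect of its own. The near/away analysis should therefore be labelled supportive only.

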6.3 Sample Size Determination

This is a pilot study to evaluate the difference in tumor microenvironment subpopulation in AI-sensitive vs. AI-resistant HR+ breast cancer. Therefore, power calculation will not be required.
Statistical Methods

Secondary analysis: Sequenced data will go through secondary analysis in department of bioinformatics in Mayo Clinic Rochester campus. The estimated duration is 3 weeks for this analysis.

Tertiary analysis: The last step of data analysis will be performed by myself and our collaboration partners of [name] and [name].

Endpoints

Specific Aim 1: To comprehensively evaluate differences in tumor microenvironment subpopulations in AI-sensitive vs. AI-resistant HR+ breast cancer.

Specific Aim 2: To assess the effects of estrogen deprivation on the immune microenvironment.

- Sub Aim 2A: To assess the effects of estrogen deprivation on the systemic immune response.
- Sub Aim 2B: To assess the effects of estrogen deprivation on tumor immune microenvironment.

7 Safety and Adverse Events

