SOP	Standard Operating Procedure

Study Summary

Title	Comprehensive Single-Cell Transcriptional Analysis of Aromatase Inhibitor-Resistant Breast Cancer
Running Title	Single cell sequencing for aromatase inhibitor-resistant breast cancer.
Phase	Pilot
Subject Participation Duration	2-8 weeks
Single or Multi-Site	Single site
Objectives	To comprehensively evaluate differences in tumor microenvironment subpopulations in AI-sensitive vs. AI-resistant HR+ breast cancer.
Number of Subjects	50 patients
Diagnosis and Main Inclusion Criteria	
1. Female \geq 18 years.2. Postmenopausal and suitable to receive aromatase inhibitor as per physician's discretion.3. Histologically confirmed un-resected operable invasive adenocarcinoma of the breast \geq 0.5 cm with estrogen receptor (ER) and/or progesterone receptor (PR) positive \geq 10%, and no human epidermal growth factor receptor 2 (HER2) amplification or overexpression.4. Patients must not have received any prior chemotherapy, radiation therapy, or endocrine therapy for their current breast cancer. Patients who received tamoxifen or raloxifene or another agent for prevention of breast cancer may be included.
Study Product, Dose, Route, Regimen	Letrozole 2.5 mg oral daily (standard of care)
Duration of Administration	2-8 weeks
Reference therapy	N/A
Statistical Methodology	This is a pilot study to evaluate the difference in tumor microenvironment subpopulation in AI-sensitive vs. AI-resistant HR+ breast cancer.

1 Introduction

This document is a protocol for a human research study. This study will be carried out in accordance with the applicable United States government regulations and Mayo Clinic research policies and procedures.

Aromatase inhibitor is currently the cornerstone standard of care endocrine therapy for patients with hormone receptor positive breast cancer. This is a pilot study to evaluate in-depth transcriptomic analysis using single cell sequencing technology to evaluate the effects of aromatase inhibitor not only in cancer breast cell but also noncancerous cells in the tumor microenvironment.

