1.2 Investigational Agent

Letrozole is an aromatase inhibitor, which is a commonly used endocrine therapy for breast cancer as per standard of care. Letrozole is an oral agent commonly supplied as a tablet.

2 Study Objectives

Our approach is to study the impact of AIs on not only cancerous cells but also on noncancerous cells in the tumor microenvironment. We seek to characterize factors discriminating non-responders from responders to AI early during treatment by analyzing different cells. We also aim to work on the impact of AIs on the immune landscape, as a noncancerous cell subpopulation, of AI-sensitive and AI-resistant tumors. This, we believe, will contribute to the current knowledge to improve the therapeutic efficacy of current treatment modalities, including chemotherapy and immunotherapy. Accordingly, we hypothesize that snRNA-seq can uncover hidden transcriptomic heterogeneity and underlying preexisting mechanisms driving AI resistance when analyzed at the single-cell level. Moreover, our research will also shed more light on the impact of estrogen deprivation on the immune landscape with AI treatment.

Primary Objective

1. To comprehensively evaluate differences in tumor microenvironment subpopulations in AI-sensitive vs. AI-resistant HR+ breast cancer.

Secondary Objective

1. To assess the effects of estrogen deprivation on the systemic immune response.
2. To assess the effects of estrogen deprivation on tumor immune microenvironment.

3 Study Design

This is a pilot study to evaluate the effects of aromatase inhibitor using single cell sequencing technology to evaluate both cancerous cells and tumor microenvironment.

[figure not shown]

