3.1 General Description

This is a prospective study to collect tissue samples from patients with early-stage hormone receptor-positive HER2-negative breast cancer. Patients with newly diagnosed hormone receptor-positive HER2-negative invasive breast cancer will be approached by the study team prior to surgery. If there is no indication for neoadjuvant therapy and the patient can proceed with surgery, the patient will be registered and start on aromatase inhibitor with letrozole 2.5 mg oral daily for 2-8 weeks until surgery as part of their standard of care. Both archival biopsy and surgical specimens will also be collected for single-cell sequencing. For patients who screen fail and do not consent to future research, tissue and blood will be discarded.

Peripheral blood prior to and after letrozole treatment will also be collected.

Estrogen receptor, progesterone receptor, HER2, and Ki-67 will be evaluated in both biopsy and surgical specimens as per standard of care. Tumors with persistent elevation of Ki-67 $\geq 10\%$ after

2-8 weeks of letrozole will be classified as non-responders, and tumors with Ki-67 < 10% after treatment will be classified as responders.

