3.4 Primary Study Endpoints

To comprehensively evaluate differences in tumor microenvironment subpopulations in AI-sensitive vs. AI-resistant HR+ breast cancer.

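### Does the primary aim need one named tissue contrast and a stated unit of analysis before this pilot's results can be interpreted?

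*Combined protocol and SAP*

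**What the plan says.** Section 3.4 gives the primary endpoint as the objective itself: "To comprehensively evaluate differences in tumor microenvironment subpopulations in AI-sensitive vs. AI-resistant HR+ breast cancer". The Statistical Methodology row of the Study Summary adds only "This is a pilot study to evaluate the difference in tumor microenvironment subpopulation in AI-sensitive vs. AI-resistant HR+ breast cancer", and Section 6.3 uses that sentence to explain why there is no power calculation. The Statistical Methods text then covers place, duration and personnel, ending with "Tertiary analysis: The last step of data analysis will be performed by myself and our collaboration partners of" two partners whose names are removed. It gives no contrast, model, unit or multiplicity rule.

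Other sections describe the comparison in different terms:

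- Section 2, hypothesis: single-nucleus sequencing can reveal "underlying preexisting mechanisms driving AI resistance".
- Section 2, approach: the study looks for "factors discriminating non-responders from responders to AI early during treatment".
- Section 1.1, Figure 1 caption: "surgical specimens from good responders and bad responders (progressors) will be analyzed and compared with pre-treated samples".
- Section 1.1, opening text: the material is "pre-treatment and post-treatment tumor samples obtained from AI-sensitive vs. AI-resistant patients".

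Response is set from Ki-67 after letrozole (Section 3.1): "tumors with Ki-67 < 10% after treatment will be classified as responders", and those at 10% or above are non-responders. Tumor tissue is collected twice, from the diagnostic biopsy and at surgery (Section 6.1). Enrolment is capped at 50 (Section 3.2).

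**The concern.** Read together, the hypothesis points to biopsy tissue compared between groups, the approach sentence can be read as surgical tissue compared between groups, and the figure caption suggests change from biopsy to surgery. These are different questions. A difference that precedes treatment and stays constant does not appear in the change contrast. A difference that arises only under letrozole does not appear in the biopsy contrast and cannot support a claim about mechanisms already present. With none of the three ranked, a reader could worry that whichever one shows something will be reported as the primary result.

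The unstated unit adds to this. Single-nucleus data yield many nuclei per patient, and treating them as independent would overstate the evidence. If both worries were borne out, the study's main result would be hard to interpret.

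**Working it through.** **The plan's own figure.** There is nothing to reproduce. The cap of 50 has no derivation, and no significance level, power, effect size, SD or group split is stated. Everything numerical below therefore rests on assumptions.

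**Do the contrasts really differ?** Assumed: patient as unit, two-sided 5% tests, SD 1 at each time, 10 non-responders and 40 responders, pre/post correlation r = 0.5 (range 0.3 to 0.7).

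- Standard error of a between-group difference at one time: √(1/10 + 1/40) = √0.125 = 0.354 SD.
- SD of change: √(2(1 − r)) = 1 at r = 0.5, so the change contrast has the same standard error there.
- Approximate power for a 1 SD difference: Φ(1/0.354 − 1.96) = Φ(0.87) = 0.81.

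Simulation with t-tests (40,000 datasets per setting) gives the proportion significant:

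| True state | Biopsy | Surgery | Change |
|---|---|---|---|
| 1 SD at both times | 79% | 79% | 5% |
| 1 SD at surgery only | 5% | 79% | 79% (65% at r = 0.3, 95% at r = 0.7) |

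With no true difference, each contrast is significant in 5%. For at least one of the three, independence would give 1 − 0.95³ = 14.3%. Allowing for their correlation, simulation gives 12.1% to 12.4% per subpopulation over r = 0.3 to 0.7 and splits 5 vs 45, 10 vs 40 and 25 vs 25.

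So the contrasts answer different questions, and each one is valid for its own. The 12% is an error rate of the trial only if a significant result on any one contrast counts as success. The plan has no such rule.

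**Do the passages contradict each other?** The objective has the same content in the Study Summary, Section 2, Section 3.4 and Aim 1 of Section 6.3. The other descriptions come from a hypothesis, a sentence on approach and a schematic of the whole study; none claims to define the primary endpoint. The layout in Section 1.1, two tissue times by two response groups, contains all three contrasts. Two of the readings are also uncertain:

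- Early during treatment may describe when response is judged rather than when tissue is taken. Section 1.1 also speaks of markers that predict response, which suits biopsy tissue.
- The effect of estrogen deprivation on the tumor immune microenvironment is a secondary objective (Section 3.5, and Sub Aim 2B in Section 6.3). It is naturally a before/after question, so the caption's comparison may serve that aim, at least for immune cells.

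**Figures that should not be counted.**

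- *Nuclei as independent.* At 100 nuclei per patient and within-patient correlation 0.01, the design effect is 1 + 99 × 0.01 = 1.99 and a nominal 5% test has true size 2 × (1 − Φ(1.96/√1.99)) = 16.5%. The plan describes no such analysis. A patient-level t-test stayed at 4.4% to 6.0% in simulation (2,000 runs, 15 vs 35).
- *Testing change separately in each group.* If both groups change by 0.6 SD (10 vs 40, r = 0.5), exactly one is significant in 59%, against 5% for a direct comparison of change. The plan does not say change will be tested this way.
- *Label and tissue from the same specimen.* A surgical score correlated 0.2, 0.3 or 0.5 with Ki-67 is significant in 16%, 31% or 72%. These are detection rates for real associations with Ki-67-defined response, which the study sets out to find. They are not false positives.

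**What would naming one contrast gain in precision?** Nothing. At 80% power the detectable difference at one time point is 0.81 SD at 25 vs 25, 1.01 SD at 10 vs 40 and 1.35 SD at 5 vs 45, whichever tissue sample is called primary.

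**The case for a change.** The strongest case for a change is that pilot status excuses the absent power calculation but not an absent contrast. The study states a hypothesis and names a primary endpoint, and a reader should be able to tell which result answers them. Only the biopsy contrast bears directly on mechanisms that precede treatment. A few sentences would settle this and the unit, with no extra patients, samples or sequencing.

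Much of that stands. The time point and the unit are unstated, the contrasts can disagree as the table shows, and the wording would cost little. But it identifies something left unsaid, not something stated that fails. All three contrasts may be intended, and an amendment demanding one primary contrast would leave the choice to the sponsor. Section 1.1 compares patients and Section 3.1 labels each tumor once, so the patient is the natural unit even without a sentence saying so.

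The supplied text may also be incomplete. References 7 to 12, which include single-cell analysis methods, are not cited anywhere in the body; a paragraph in Section 1.1 begins mid-sentence; and Statistical Methods opens at secondary analysis with no primary step. A bare reference list fixes neither the contrast nor the unit, but these signs weaken any claim that the methods were never written.

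**Conclusion.** No change is called for. This is a documentation gap in an exploratory pilot of up to 50 patients, and analysts can fill it sensibly: summarise or model per patient, keep biopsy and surgical samples paired, compare change directly between groups, report all three contrasts, and rest any statement about pre-existing mechanisms on biopsy tissue.

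The choice of contrast matters for interpretation (79% against 5% detection for a constant 1 SD difference at 10 vs 40 and r = 0.5, both assumed). No rule, number or test in the plan is shown to produce a wrong result, and the passages do not contradict one another. The 12% chance of at least one nominally significant contrast per subpopulation would matter only if significance on any of them were a success criterion, and none is set.

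The conclusion rests on the study being read as a pilot without a confirmatory claim. If one contrast were later presented as a confirmatory primary result, the missing ranking would become a real weakness.
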